Subjects will consist of a convenience sample of emergency department patients that require US-guided IV access. Eligible patients must be greater than 18 years old, and be self-identified as a difficult stick. The patient must also recount a prior emergency room visit or hospitalization in which more than 2 attempts were required to obtain access, have a history of a rescue catheter as the result of an inability to obtain a peripheral IV, or have one of the following conditions: end-stage renal disease on hemodialysis, IV drug abuse, or sickle cell disease.

Patients are excluded if they do not meet inclusion criteria, have participated in the study prior, have already undergone an attempt at vascular access or if the enrollment process has the potential to delay their care. Study participation is voluntary and written informed consent will be obtained. See Appendix A for Eligibility Checklist.

Numerous emergency room staff members are proficient in placing ultrasound-guided IVs. This includes physicians, nurses, and technicians. Staff will be enlisted on a voluntary basis to perform insertions on a voluntary basis.

Study Procedure:

Initial Assessment

Post-consent, eligible patients will be randomly allocated to the experimental group (forearm) or the control group (upper arm) in a ratio of 1:1 via a computer-generated randomization schedule. Research staff at the Department of Biostatistics will perform concealed immediate assignment by following a block scheme. Sealed envelopes containing the randomized IV access arm will be revealed at the bedside.

After patient enrollment, the insertion nurse or physician is engaged to perform the procedure. Only providers that are credentialed in ultrasound-guided vascular access will place catheters in study subjects. Vessel depth and diameter are measured by research staff and images are saved and archived for review by the Emergency Ultrasound Director. Vessel depth is measured on the ultrasound unit from the point of contact to the middle of the vein. All catheters are 20 gauge in diameter. The research staff will direct the inserter to choose the basilic, cephalic or brachial vein at least 2 cm above the antecubital fossa. If the patient is randomized to the control group, the inserter will place the Standard Long 4.78 cm catheter. If the patient is randomized to the experimental group, the inserter will place the Ultra Long 6.35 cm IV.

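### The plan does not fix the inserter before the envelope is opened, so operator choice could follow allocation in a trial with no blinding described

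*Combined protocol and SAP*

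**What the plan says.** All of this is in the combined protocol and SAP.

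- **Allocation** (Study Procedure, Initial Assessment): "Post-consent, eligible patients will be randomly allocated" in a 1:1 ratio. "Research staff at the Department of Biostatistics will perform concealed immediate assignment by following a block scheme". No stratification factor is named. "Sealed envelopes containing the randomized IV access arm will be revealed at the bedside".
- **Inserter** (next paragraph of the same section): "After patient enrollment, the insertion nurse or physician is engaged to perform the procedure". The sentence after it limits insertion to providers credentialed in ultrasound-guided vascular access.
- **Inserter pool** (end of Study Population and Eligibility): of the proficient emergency staff, "This includes physicians, nurses, and technicians"; then "Staff will be enlisted on a voluntary basis to perform insertions on a voluntary basis". The procedure paragraph mentions only a nurse or a physician. Study Site adds that nearly forty ancillary staff are certified.
- **Data**: Study Procedure lists inserter details and need for a rescue inserter among the variables collected. Appendix B has ID fields for a first and a second inserter, but no field for role and no statement of when the ID is entered.
- **Analysis**: Study Design plans exploratory adjusted analyses of the primary objective without naming covariates. The Cox models in Statistical Analysis are aimed at catheter variables. Neither section mentions the inserter.
- **Blinding**: none is described, and the inserter necessarily knows which catheter is being placed.

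**The concern.** Concealed allocation protects the choice of which patient enters which arm. It does not protect a choice made after the arm is revealed. If the operator can be chosen at that stage, the arms may differ in who placed the catheter as well as in which catheter was placed, and the log-rank comparison would attribute both differences to catheter length.

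The endpoints are exposed to this. Insertion angle and length of catheter in the vein depend partly on technique, and the preliminary data tie length in vein to survival. First-stick success, number of attempts and time to insertion are listed objectives and reflect operator skill directly.

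There is also a plausible reason for operator choice to depend on the arm. The background says that the 4.78 cm catheter is the longest one stocked at this institution, so the 6.35 cm catheter may be less familiar to staff. That could draw more experienced operators to the ultra long arm, which would flatter it. If instead operators in that arm were less practised, the bias would run the other way and hide a benefit.

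**Working it through.** **1. What order does the text give?** The steps appear as consent, allocation, bedside reveal, then engagement of the inserter after enrollment. Two readings fit:

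- Enrollment covers consent, allocation and reveal. The inserter is then chosen with the arm known.
- Enrollment means consent only. The inserter may already be at the bedside when the envelope is opened.

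Paragraph order favours the first reading, but no sentence settles it. Under either reading, nothing requires the operator to be fixed before the reveal.

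**2. What already limits the problem?** Credentialing applies equally to both arms and narrows the range of skill without making experience equal. Recorded inserter details allow imbalance to be described. Adjustment by individual inserter would be thin: if about 40 ancillary staff shared the 182 planned insertions equally, 182 / 40 = 4.6 patients each, and fewer once physicians are counted. An inserter chosen after the reveal would also be a post-allocation variable, not a baseline covariate.

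**3. How large could it be?** The plan has no operator figure to reproduce. Its only figure used here is the planned hazard ratio of 0.63 (Sample Size and Power Analysis), as a yardstick. All other inputs are assumptions:

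- h: failure hazard of more skilled relative to other operators
- a, b: share of catheters placed by more skilled operators in the ultra long and standard arms

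With no device effect, the spurious hazard ratio is approximately (a·h + 1 − a) / (b·h + 1 − b).

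| h | a | b | Calculation | Spurious HR | Shares reversed |
|---|---|---|---|---|---|
| 0.7 | 0.6 | 0.4 | 0.82 / 0.88 | 0.93 | 1.07 |
| 0.7 | 0.7 | 0.3 | 0.79 / 0.91 | 0.87 | 1.15 |
| 0.5 | 0.6 | 0.4 | 0.70 / 0.80 | 0.875 | 1.14 |
| 0.5 | 0.7 | 0.3 | 0.65 / 0.85 | 0.76 | 1.31 |

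On the same approximation, a true 0.63 would appear as 0.63 × 0.93 = 0.59 or 0.63 / 0.93 = 0.68 in the mildest row. In the most extreme row it would appear as 0.63 × 0.765 = 0.48 or 0.63 / 0.765 = 0.82.

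**4. Does the approximation hold over follow-up?** The formula ignores the change in mix as catheters placed by weaker operators fail first. A second calculation allows for this by comparing events per unit of catheter time between arms. It uses exponential failure, λ = ln 2 / 30 per hour (the plan's 30-hour control median, applied here to the more skilled operators) and an assumed 120 hours of follow-up. With q the share placed by less skilled operators and r their relative hazard:

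- events = q(1 − e^(−λr·120)) + (1 − q)(1 − e^(−λ·120))
- catheter time = q(1 − e^(−λr·120)) / (λr) + (1 − q)(1 − e^(−λ·120)) / λ

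For r = 2 (the same as h = 0.5), a 40% versus 60% split gives 0.87 and a 30% versus 70% split gives 0.76, matching the table. For r = 1.25 and 1.5, the 40% versus 60% split gives 0.96 and 0.92. With an equal mix, a true 1.00 stays at 1.00 and a true 0.63 appears as 0.63 to 0.64.

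**5. What imbalance would chance produce?** After 10% dropout, 182 × 0.9 = 163.8, about 82 per arm. If half of all insertions are by one type of operator, the 95% limit for the difference in share is 1.96 × √(2 × 0.25 / 82) = 0.153, about 15 percentage points. A 60/40 split (20 points) would exceed this, so reporting operator mix by arm would be informative.

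**The case against.** The strongest reply is that the plan does not say the operator is chosen after allocation. The sentence says only that the inserter is engaged after enrollment, and a bedside reveal is compatible with an inserter already present. This stands. A reader might infer from paragraph order that operators are picked with the arm known. The text permits that but does not state it.

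A reader might also infer that staff volunteer patient by patient and can accept or decline once they know the device. The documents say only that enlistment is voluntary, which could mean once for the whole study. Nor do they describe research staff calling a more experienced colleague for the longer catheter. Operator unfamiliarity with that catheter is itself inferred from what the site stocks.

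It would also be too strong to say that the plan disagrees on who is qualified. One credentialing rule covers all inserters. The mismatch is one of professional group, with technicians in one description and absent from the other, and either list would apply equally to both arms.

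Finally, inserter details are collected and adjusted analyses are planned, so an imbalance could be described and explored. That is partial protection, because inserter is not among any named covariates. None of these replies supplies a rule that fixes the operator before the reveal.

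**Conclusion.** The point holds as a gap in procedure and a possible bias; no bias has been shown. The plan has no inserter assignment rule, no stratification by inserter and no requirement to fix the operator before the envelope is opened. Operator choice could therefore follow the arm and affect catheter survival and the placement endpoints, in either direction.

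The size is unknown. The spurious hazard ratios of 0.76 to 0.93, or 1.07 to 1.31 in reverse, rest entirely on assumed operator effects (0.5 or 0.7) and assumed splits (60/40 or 70/30). The milder cases are small beside the planned 0.63; the most extreme is not. They show that the issue can matter and do not predict that it will. The documents do not support concluding that the arms will differ in operator skill, or that the result would favour the longer catheter.

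This is a cheap improvement. The technician wording is a minor reconciliation.

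**What to change.** - In Study Procedure, Initial Assessment, state that the credentialed first inserter is identified, accepts the case and is entered in Appendix B as Inserter #1 ID, with role and time of entry, before the envelope is opened.
- State that any later change of first inserter is recorded as a deviation and reported by arm. A hand-over to a second provider after failed attempts, which the plan already allows, remains under the existing rescue-inserter field.
- Reconcile the two descriptions of the inserter pool, so that Study Population and Eligibility and Study Procedure name the same professional groups.
- Optionally, add a sensitivity analysis adjusting the arm effect for first-inserter role. It adds little once the operator is fixed before the reveal, and role need not track experience among credentialed staff.

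The cost is one reordered step and a role and time entry on Appendix B, with no extra patients or procedures. The downside is a possible delay of a few minutes at the bedside while the inserter is found. The procedure time on Appendix B starts when the needle meets the skin, so that wait would not enter it.

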Staff members are expected to attempt a minimum of 3 attempts before enlisting another provider for help. A functional IV is confirmed by extraction of 5 mL of nonpulsatile blood and low-resistance infusion of a 5 mL normal saline flush without evidence of extravasation. Other data variables collected include: inserter details, need for rescue inserter, patient pertinent medical history, vitals, age, sex, first-stick success, cannulation success or failure, vein diameter, catheter in vein longitudinal measurement, angle of insertion, number of venous access attempts, time of IV insertion, time to IV insertion, location of IV insertion, distance of IV insertion from the antecubital fossa, medications infused, ionic contrast injection for computed tomography. A venous access attempt is defined as each time the needle punctures the skin. Once the IV is secured, research staff will measure distance from the puncture or catheter insertion site to the antecubital fossa to quantify the site to antecubital measurement. See Appendix B for Data Collection Tool for insertion-related variables.

Follow-up Assessment

After initial assessment, the catheter will be assessed by the research team every 24 hours as long as the patient is hospitalized. At each follow up interval the researcher notes the date/time of evaluation and assesses for any signs and symptoms of complications and functionality of the device. A catheter is functional if the IV flushes without resistance. Catheters will be assessed daily for signs and symptoms of complications. See Appendix C for details regarding the assessment for functionality and complications. Any signs or symptoms of complications or lack of functionality will be reported to the patient's primary care team so that management of the IV catheter can be addressed.

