If the catheter was identified to have any signs or symptoms of complications during follow-up assessment the date and time of observation of the complication will be documented in the data collection tool and the primary team will be notified of the complication. If the catheter was removed prior to the follow-up assessment then the IV removal time and the reason for removal will be obtained through chart review. For all catheters removed due to a complication, re-insertion attempt data will be tracked through the medical record in the nursing section for venous lines and need for reinsertion of the IV or escalation to a midline, PICC, or CVC will be noted. If the patient is discharged prior to the time of follow-up assessment then the time of discharge will be documented and the IV will be presumed functional until time of discharge unless otherwise noted in the chart.

The medication administration record will be queried for all medications given through each catheter. Vesicants/irritants that are generally given via central line or considered caustic to the vessel will be noted in both groups. Number of doses will be recorded. See Appendix D for full list of non-neoplastic vesicants/irritants.

Additional data gathered by research staff on follow-up evaluation includes: dwell time in days/hours, hospital length of stay, and number of peripheral IVs or rescue catheters for duration of stay.

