Appendix E represents the data collection documentation tool for all medications.

SVT and DVT rates will be calculated based on upper extremity proven diagnosis of SVT and/or DVT in symptomatic cases. Researchers will review all study subject records in EPIC and screen for all upper extremity venous Doppler examinations. Radiology interpretations will be reviewed for findings of consistent with thrombus. This review will occur thirty days post patient discharge.

Infection rate will be tracked using confirmed blood stream infection data from epidemiology. These are cases in which line sepsis or bacteremia is confirmed by positive blood cultures.

Cost difference between approaches will be tracked. Equipment costs and personnel costs will be tracked. Number and type of IV catheters inserted/attempted will be extracted from the medical record. Supply costs will be estimated based on number of IVs attempted. Median time to successful catheter placement will serve as a baseline for estimating time needed for future reinsertions. Time will be assigned a monetary value. We will also track the number of patients from each group that require a PICC or CVC as a rescue catheter.

Sample Size and Power Analysis:

For this randomly allocated two-groups experiment, the primary outcome is catheter survival. Sample size calculation is based on primary outcome: composite or all cause premature removal due to complication of the IV catheter. Based on literatures and a new published article immediately prior to study period, we estimate sample size using the median survival time 30 hours for the 4.78 cm standard IV option. 91 subjects per group for a total sample size of 182 subjects is the minimum recommendation assuming a 10% dropout rate. This calculation

achieves power of 80% to detect a hazard ratio of 0.63 or less for line failure of the 6.35 cm ultra long IV based on log-rank test.

Statistical Analysis:

Characteristics of enrolled and eligible patients will be summarized between two arms using means [standard deviations] and medians [interquartile ranges] compared by t-tests or Wilcoxon tests for continuous variables and frequencies (percentages) compared by chi-squared tests or Fisher's exact tests for categorical variables.

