Survival analysis methods (Kaplan-Meier curves, the log-rank test for continuous failure times or logistic model for discrete failure times) will be used for analyzing times to IV failure with non-failure times treated as censored. Proportions of SVT, DVT and catheter infection rates will be reported separately for each arm. Nonparametric summaries and a Wilcoxon Rank sum test will be used for the cost data. To test the effect of catheter variables on survival, we will further use Cox proportional hazard regression models for time-to-event outcomes and logistic regression models for binary outcomes. P-values of less than 0.05 will be considered statistically significant. Analysis will be conducted using SAS 9.4.

Study Site:

William Beaumont Hospital, Royal Oak (RO) campus is the proposed site for the investigation. It is a 1,100 bed major academic and referral center with Level 1 adult trauma and Level 2 pediatric trauma status. A major teaching facility, Beaumont, Royal Oak has 55 residency and fellowship programs with 454 residents and fellows. Beaumont is the exclusive clinical partner for the Oakland University William Beaumont School of Medicine. The Beaumont Research Institute was established more than 30 year ago at Royal Oak and offers research support services to clinical investigators.

The Royal Oak (RO) Emergency Center (EC) has the resources available to complete this project. This site is a tertiary care, level I trauma center with an annual ED census greater than 130,000 visits. I collaborated with nursing leadership in 2015 and implemented an ancillary staff-training program for placing US-guided IVs. Nearly forty ancillary staff members are certified in this procedure. Further, weekly logs of IVs placed under US-guidance show that an average of 10 US-guided IVs are placed daily. The RO EC has 130,000 annual visits of which many patients have difficult access. We also have 11 portable US machines with high frequency linear transducers that are ideal for vascular imaging.

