Appendix B: Insertion-Related Data

Research Staff completing form (signature/date): _____

Catheter Type (circle): Ultra Long IV Standard IV

	Depth (cm)	Diameter (cm)	# Attempts	Depth (cm)	Diameter (cm)	# Attempts
	1 st Venous Access point				2nd Venous Access point	
Inserter #1 ID:						
	1 st Venous Access point				2nd Venous Access point	
Inserter #2 ID:						

[figure not shown]
Minutes for procedure completion (time from needle to skin to dressing site): _____

Time at Completion of Insertion: _____

Initial EC Vitals: BP _____ HR _____

Gender: _____ Age: _____ BMI: _____

Location of Successful Cannulation
(Mark 1/2/3 for access attempts, circle successful site): Left Right

Insertion site distance from AC fossa (cm): _____

Disposition (Circle): Observation Regular Progressive ICU Discharge

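### No masking of outcome ascertainment is described once the arm is revealed, although the primary event turns on judgements about flushing, complications and the reason for removal

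*Combined protocol and SAP*

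**What the plan says.** All references are to the combined protocol and SAP.

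- **Study Procedure, Initial Assessment.** Assignment is concealed in sealed envelopes that are opened at the bedside. Research staff measure the vessel and guide the choice of site: "The research staff will direct the inserter to choose the basilic, cephalic or brachial vein".
- **Appendix B.** Research staff sign the insertion form, which carries the line "Catheter Type (circle): Ultra Long IV Standard IV".
- **Study Procedure, Follow-up Assessment.** After insertion, "the catheter will be assessed by the research team every 24 hours as long as the patient is hospitalized". The function criterion is "A catheter is functional if the IV flushes without resistance". Complications or loss of function are reported to the primary care team so that it can manage the catheter. For a catheter removed before the next check, "the IV removal time and the reason for removal will be obtained through chart review".
- **Appendix C.** This lists function codes (draw, flush, infusing, failed) and eight removal reasons, among them completion of therapy, pain, leaking, other and unknown. It gives codes without criteria. A post-processing block holds angle of insertion, length in vein and percent length in vein.
- **Sample Size and Power Analysis; Statistical Analysis.** The primary outcome is premature removal due to complication. Times without failure are censored, and the arms are compared by the log-rank test.

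No section describes a masked assessor, arm-blind coding of removal reasons, adjudication, or a sensitivity analysis for ascertainment.

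**The concern.** Concealing the allocation protects assignment. It does not protect judgements made after the envelope is opened. Three later steps leave room for judgement: whether a flush met resistance, whether a sign counts as a complication, and whether a charted removal is coded as completion of therapy or as a complication. The last code alone separates an event from a censored time.

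The study's stated aim is to show better survival with more catheter in the vein, so the expected winner is known to the team. If the threshold for calling, reporting or coding a failure differed between arms, even without intent, the difference would pass directly into the hazard ratio. A difference in reporting could also change actual removals, because the report goes to the people who manage the catheter. Such an error cannot be separated from a catheter effect after the data are collected.

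**Working it through.** **Inputs from the documents.** Significance level 0.05 ("P-values of less than 0.05 will be considered statistically significant"), taken as two-sided because the sidedness is not stated. Power and effect: the sample size "achieves power of 80% to detect a hazard ratio of 0.63 or less for line failure". Control "median survival time 30 hours for the 4.78 cm standard IV option". Total 182, 1:1, 10% dropout. Pilot failures 29 of 86 (Preliminary Data).

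**The plan's own figure.** Schoenfeld's formula for the number of failures is

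d = 4(1.96 + 0.8416)² / (ln 0.63)² = 4 × 7.849 / 0.2135 ≈ 147 (148 if rounded up).

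After dropout, 182 × 0.9 = 163.8, about 164 patients. The 182 therefore needs about 148/163.8 = 90% of them to fail. The plan states neither an event probability nor a follow-up length, so 182 cannot be confirmed. It has no bearing on masking and is used here only to set the upper event count. For a lower count, the pilot fraction gives 164 × 29/86 ≈ 55.

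**Illustration 1: failures missed in one arm (rates assumed).** Suppose there is no true difference, and a share u of failures in the ultra long arm only is never recorded, being censored instead, as when a complication is coded as completion of therapy. Then:

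- apparent hazard ratio = 1 − u
- recorded failures d = d₀(1 − u/2)
- mean of Z = |ln(1 − u)| × √d / 2
- two-sided error = P(|Z| > 1.96)

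Example, d₀ = 147 and u = 10%: d = 139.65; mean Z = 0.1054 × 11.82 / 2 = 0.623; error = 0.0905 + 0.0049 = 0.095.

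| u | Apparent HR | Error, d₀ = 147 | Error, d₀ = 55 |
|---|---|---|---|
| 5% | 0.95 | 0.061 | 0.054 |
| 10% | 0.90 | 0.095 | 0.067 |
| 15% | 0.85 | 0.157 | 0.089 |
| 20% | 0.80 | 0.250 | 0.123 |

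**Illustration 2: failures recorded late, not lost.** Simulation with 82 per arm, exponential failure times with median 30 h, no true effect, 168 h of follow-up, about 161 failures. If 20% of ultra long failures are recorded 24 h late, the two-sided error is about 11% to 12%, against about 27% if they are lost. At 10% it is about 6% to 7%, against about 10% to 11%.

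**Illustration 3: false failure calls in the standard arm.** Simulation with 82 per arm, median 30 h, discharge censoring with median 72 h, no true effect. Wrong calls at 5%, 10% and 20% per daily check in the standard arm only give apparent hazard ratios of 0.94, 0.89 and 0.82. The chance of a significant result favouring the ultra long catheter becomes 5.6%, 10.0% and 18.4%, against a nominal 2.5%. Wrong calls at 5% in both arms give 1.00 and 2.6%: equal error creates no false difference.

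**Does Appendix C conceal the arm?** It has no catheter-type field. However, length in vein divided by percent in vein returns the catheter length. With 3.1 cm in the vein, an entry of 65% gives 3.1/0.65 = 4.77 cm (the standard catheter), and 49% gives 3.1/0.49 = 6.33 cm (the ultra long). Once the post-processing block is filled in, the form reveals the arm.

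**The case against.** Several points on the other side stand.

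- **A reader might infer that the checker is known to be unmasked.** The documents do not say so. They speak of the research team and never state that the person who attended the insertion makes the follow-up checks. What they support is that no masking is described.
- **A reader might infer that the report-to-removal route is itself a bias.** It applies to both arms. It distorts the comparison only if reporting, or the treating team's response, differs by arm, and nothing in the documents shows that it does.
- **A reader might extend the point to thrombosis and infection.** Those endpoints rest on radiology interpretations and on infections confirmed by positive blood cultures. They are largely objective and are not part of this point.
- **Much of the event lies outside the research team's hands.** The primary team manages the catheter, and reasons for removals between checks come from the chart. This limits what the research team can influence. It also limits the remedy, because arm-blind coding cannot undo an unmasked chart entry.
- **The criterion is not wholly open.** The objectives set a 5 mL flush, and the draw and infusing codes are firmer than resistance.
- **The table is a one-directional case.** A stiff flush that is accepted today is checked again a day later, so permanent loss is the harsher assumption. At 55 failures and u of 5% to 10%, the error of 5% to 7% is close to nominal.

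These points narrow the concern but do not remove it. The removal code still decides event or censoring, and nothing in the plan keeps the arm from whoever assigns it.

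**Conclusion.** The concern holds in a limited form and should be acted on. The plan describes no masking of any step between the opening of the envelope and the coding of the primary event, and those steps involve judgement. The documents do not show that bias will occur, in which direction, or how large it would be.

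The error range of 6% to 25% (147 failures) or 5% to 12% (55 failures) rests on three assumptions: no true effect, error confined to the ultra long arm, and permanent loss of 5% to 20% of its failures. None of these rates comes from the documents. Delayed recording gives smaller figures at the higher event count. Confidence is medium. The case for change is that the safeguard is cheap now and the error, if present, cannot be repaired later. Masking would not alter the sample size.

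**What to change.** Use the existing research team.

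1. **Coding.** A team member who is not told the arm codes removal time and removal reason (completion of therapy versus complication) against study ID, as far as the chart allows.
2. **Daily checks.** Where the rota allows, a team member who did not attend that patient's insertion makes the check. The checker does not receive Appendix B. Move the Appendix C post-processing block (angle, length in vein, percent length in vein) to a separate form.
3. **Sensitivity analysis.** Record at each check whether the checker knew the arm. Repeat the log-rank analysis with each failure first identified at an unmasked check timed instead at the next masked check or the charted removal for complication, whichever comes first, and censored at last observation if neither occurs.

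Reporting of problems to the primary team is unchanged. For that reason step 3 tests how failures are recorded, but it cannot undo a removal prompted by an unmasked report.

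The cost is protocol wording, one split form and a scheduling constraint, with no new assessor. Masking will be imperfect if the chart or the dressed catheter reveals the length. Both catheters are 20 gauge, but whether they look alike once dressed has to be confirmed.
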